## Appendix P: Criteria for Response assessment in Myelodysplasia (based on modified IWG guidelines)

Category	Response Criteria
Complete remission	
Bone marrow: <math>\leq 5\%</math> myeloblasts with normal maturation of all cell lines*
 
Persistent dysplasia will be noted*
 
Peripheral blood
 
Hgb <math>\geq 11</math> g/dL
 
Platelets <math>\geq 100 \times 10^9/L</math>
 
Neutrophils <math>\geq 1.0 \times 10^9/L</math>
 
Blasts 0%

Partial remission	
All CR criteria if abnormal before treatment except:
 
Bone marrow blasts decreased by <math>\geq 50\%</math> over pretreatment but still <math>> 5\%</math>
 
Cellularity and morphology not relevant

Marrow CR	
Bone marrow: <math>\leq 5\%</math> myeloblasts and decrease by <math>\geq 50\%</math> over pretreatment
 
Peripheral blood: if HI responses, they will be noted in addition to marrow CR

Stable disease	Failure to achieve at least PR, but no evidence of progression for $> 8$ wks
Failure	Death during treatment or disease progression characterized by worsening of cytopenias, increase in percentage of bone marrow blasts, or progression to a more advanced MDS FAB subtype than pretreatment
Relapse after CR or PR	
At least 1 of the following:
 
Return to pretreatment bone marrow blast percentage
 
Decrement of <math>\geq 50\%</math> from maximum remission/response levels in granulocytes or platelets
 
Reduction in Hgb concentration by <math>\geq 1.5</math> g/dL or transfusion dependence

Cytogenetic response	
Complete - Disappearance of the chromosomal abnormality without appearance of new ones
 
Partial - At least 50% reduction of the chromosomal abnormality

Disease progression	
For patients with:
 
Less than 5% blasts: <math>\geq 50\%</math> increase in blasts to <math>> 5\%</math> blasts
 
5%-10% blasts: <math>\geq 50\%</math> increase to <math>> 10\%</math> blasts
 
10%-20% blasts: <math>\geq 50\%</math> increase to <math>> 20\%</math> blasts
 
20%-30% blasts: <math>\geq 50\%</math> increase to <math>> 30\%</math> blasts
 
Any of the following:
 
At least 50% decrement from maximum remission/response in granulocytes or platelets
 
Reduction in Hgb by <math>> 2</math> g/dL
 
Transfusion dependence

*Dysplastic changes should consider the normal range of dysplastic changes (modification).	

## Appendix Q: Myeloproliferative Neoplasm (MPN) Symptom Assessment Form Total Symptom Score (MPN-SAF TSS)

Name: \_\_\_\_\_ Date: \_\_\_\_\_

Fill out the form below to track the burden of your symptoms.

For each symptom, please circle the number that best describes how severe that symptom is, on a scale of 0 to 10, with 0 being absent or as good as it can be and 10 being worst imaginable. Make sure you circle a number for every symptom. Be sure to share your answers with your haematologist or other healthcare professional.

**Symptom - 1 to 10, 0 if absent and 10 being worst imaginable**

Please rate your fatigue (weariness, tiredness) by circling the one number that best describes your WORST level of fatigue during the past 24 hours

Fatigue										
0	1	2	3	4	5	6	7	8	9	10
(ABSENT) (WORST IMAGINABLE)										

Circle the one number that describes how much difficulty you have had with each of the following symptoms during the *past week*

Filling up quickly when you eat (early satiety)										
0	1	2	3	4	5	6	7	8	9	10
(ABSENT) (WORST IMAGINABLE)										

Abdominal discomfort										
0	1	2	3	4	5	6	7	8	9	10
(ABSENT) (WORST IMAGINABLE)										

Inactivity										
0	1	2	3	4	5	6	7	8	9	10
(ABSENT) (WORST IMAGINABLE)										

Problems with concentration - compared to before my diagnosis										
0	1	2	3	4	5	6	7	8	9	10
(ABSENT) (WORST IMAGINABLE)										

Night sweats										
0	1	2	3	4	5	6	7	8	9	10
(ABSENT) (WORST IMAGINABLE)										

Itching (pruritus)										
0	1	2	3	4	5	6	7	8	9	10
(ABSENT) (WORST IMAGINABLE)										

Bone pain (diffuse, not joint pain or arthritis)										
0	1	2	3	4	5	6	7	8	9	10
(ABSENT) (WORST IMAGINABLE)										

Fever (> 37.8°C or 100°F)										
0	1	2	3	4	5	6	7	8	9	10
(ABSENT) (DAILY)										

Unintentional weight loss last 6 months										
0	1	2	3	4	5	6	7	8	9	10
(ABSENT) (WORST IMAGINABLE)										

To help you get a clear overall picture of how you are feeling, you can add up all your scores to calculate your Total Symptom Score.

**Total:** \_\_\_\_\_

Adapted from Emanuel RM, Dueck AC, Geyer HL, et al. Myeloproliferative neoplasm (MPN) symptom assessment form total symptom score: prospective international assessment of an abbreviated symptom burden scoring system among patients with MPNs [published correction appears in J Clin Oncol. 2012;30(36):4590]. J Clin Oncol. 2012;30(33):4098-4103

## Appendix R: Bayesian Adaptive Design Framework for the Modular Phase II Study to Link Targeted Therapy to Patients with Pathway Activated Tumors.

### 1 Introduction

This document outlines the adaptive design framework to be used for all trials within Novartis's Modular Phase II study to link targeted therapy to patients with pathway activated tumors.

Although the selected tumor types may vary by trial, this document outlines the design and analysis approach based on 8 example tumor cohorts:

- Lung NSC
- Bladder
- Breast
- Colorectal
- GIST
- HNSCC
- Ovarian
- Sarcoma

Other tumor types may be considered for trials if 1) 4 or more patients are enrolled in the cohort, and 2) a reasonable estimate of the clinical benefit rate is available.

The primary endpoint is clinical benefit rate (CBR) in each cohort, with clinical benefit being assessed at 16 weeks. All patients will receive the experimental treatment for that particular trial.

#### 1.1 Primary Analysis

We let  $Y_i$  be the response indicator for the  $i^{\text{th}}$  subject, and let  $R_g$  be the assumed probability of response within a control population and  $\pi_g = \Pr(Y_i = 1 | g_i = g)$  be the underlying probability of response for group  $g$  within the trial. We transform to the logit scale for modeling purposes. Let  $\theta_g$  be the mean log odds treatment effect, i.e.:

$$\theta_g = \log\left(\frac{\pi_g}{1 - \pi_g}\right) - \log\left(\frac{R_g}{1 - R_g}\right).$$

Thus,  $\theta_g$  is the group specific logistic regression coefficient for the treatment within group  $g$ . The primary analysis is a set of group specific tests that  $\theta_g > 0$ , meaning that the treatment is better than the assumed control rate for that group. Thus, we wish to test the set of hypotheses

$$H_{0g} : \theta_g \leq 0$$

$$H_{1g} : \theta_g > 0$$

We proceed in a Bayesian fashion, assigning a prior distribution (discussed below) and computing the posterior probability of  $H_{1g}$  within each group  $g$ . If, at the final analysis,

$$\Pr(\theta_g > 0 | \text{data}) > 0.80$$

Then group  $g$  will be declared a success (thus, the final analysis produces a separate decision for each group). The trial also allows for early stopping of groups, described below.

## 1.2 Trial Logistics

The trial will enroll all available subjects in all cohorts for 2 years unless a cohort cap is reached or a cohort is stopped early, or the trial is stopped early by Novartis. The trial will enroll no more than 30 evaluable subjects in each cohort. Interim monitoring will be conducted starting after the first 30 patients are enrolled overall (across all cohorts), and continuing each 13 weeks thereafter till study enrollment closure. After that, one CBR analysis will be done at the end of the study. At each interim data review, response information for the various groups will be evaluated to determine the current  $\Pr(\theta_g > 0 | \text{data})$  within each cohort, with sufficiently high/low values used to stop the cohort for success/futility. A minimum of 10 patients will be required in a cohort before it may discontinue enrollment for futility, and a minimum of 15 patients are required before discontinuing a cohort for efficacy. If a cohort stops enrolling early, the remaining cohorts will continue until the end of 2 years or until the other groups reach their own early stopping criteria. The final analysis will occur after the analysis of the analysis of the study data for the primary CSR.

The trial will enroll subjects in all listed cohorts. In addition, should other cohorts be identified throughout the trial, the following mechanism will be used. If another cohort is identified, it will not be placed into the statistical analysis unless 3 subjects enroll within the cohort (thus, the trial may enroll multiple possible cohorts within the “other” category, but a cohort will only be added to the list if at least 3 patients enroll from that cohort). Thus, it is possible (but not viewed as likely) that multiple additional cohorts may be added to the trial if the trial has sufficient enrollment in multiple additional cohorts. In addition to sufficient enrollment, the sponsor must have a reasonable estimate of the control clinical benefit rate.

Subjects within any cohort which does not reach the minimum 3 subject enrollment will be excluded from the interim and final analyses. As the study continues, early interim data reviews may be based on fewer cohorts than later interim data reviews, as the interim data reviews will include whatever cohorts have satisfied the criteria at the time of the data review.

## 2 Statistical Modeling

We let  $Y_i$  be the response indicator for the  $i^{\text{th}}$  subject, and let  $R_g$  be the probability of response within a control population and  $\pi_g = \Pr(Y_i = 1 | g_i = g)$  be the underlying probability of response for group  $g$  within the trial. We transform to the logit scale for modeling purposes. Let  $\theta_g$  be the mean log odds treatment effect, i.e.:

$$\theta_g = \log\left(\frac{\pi_g}{1 - \pi_g}\right) - \log\left(\frac{R_g}{1 - R_g}\right).$$

The statistical design borrows information across groups with a hierarchical model. The hierarchical model allows dynamic borrowing of information between groups such that more borrowing occurs when the groups are consistent and less borrowing occurs when the groups differ. In this way, the model is a compromise between the two alternate extremes of either a completely pooled analysis or a separate analysis in each group. We additionally incorporate a clustering mechanism that allows borrowing within clusters but treats clusters separately. This minimizes borrowing across groups that are quite different in terms of CBR.

The purpose of such an analysis (discussed in more detail in [Section 5](#)) is to produce higher power or lower type I error in situations where we see some commonality (identical effects are not required) among the groups. The model will borrow more in situations where the groups appear similar than situations where the groups appear different.

## 2.1 Hierarchical Model with Clustering

Our hierarchical approach involves two stages. The goal of both stages is to allow the data to drive the amount of borrowing across groups. If the data indicate a large amount of borrowing is appropriate (due to similar results), the model will borrow more and thus increase the overall power of the trial within each group. In contrast, if the data indicate a small amount of borrowing is appropriate (due to dissimilar results) the model will adjust and each group will stand more on its own. This “dynamic” borrowing property is distinct from other approaches which use a fixed informative prior or *a priori* assume an amount of borrowing across groups. Here the approach includes two stages to identify the appropriate amount of borrowing based on the data.

The first stage of model places the groups into distinct clusters. The purpose of this stage is to minimize borrowing of information across groups that appear to be quite different. Thus, for example, should 2 of the groups appear similar while the others differ significantly, the model may place a large probability on two clusters, one containing the two similar groups with the other containing the remaining groups. The model incorporates the uncertainty of the data in this determination, producing a probability distribution over the possible clusterings. Thus, in our example, the model may consider it highly likely that the 2 similar groups are in one cluster with the remaining groups in another, but it would also retain lower probabilities on the possibility all groups are in one cluster (e.g. we are simply seeing differences in the two groups by chance) as well as other possibilities. The complete analysis averages over this uncertainty. This clustering approach is implemented through a Dirichlet Process Mixture (DPM) model, described in the appendix.

At the second stage, we place hierarchical models over the groups within each cluster (thus, conditional on the clustering, there is no borrowing of information across clusters, only within clusters). The hierarchical model assumes that the  $\theta_g$  have an across groups distribution

$$\theta_g \sim N(\mu, \tau^2)$$

The across group mean  $\mu$  and variance  $\tau^2$  are unknown, and hence have a prior distribution which is combined with the data to produce estimates of  $\mu$  and  $\tau^2$ .

The variance component  $\tau$  controls the degree of borrowing among groups. Small values of  $\tau$  result in a greater degree of borrowing while large values of  $\tau$  correspond to less borrowing.

The parameter  $\tau$  is estimated using the data, so the observed between group variation is a key component of the model behavior.

Combined, the two stages allow groups with similar results to borrow information between them (they will have a high probability of being in the same cluster) while groups with different results will borrow far less information between them (they will have a low probability of being in the same cluster).

Details of the two stages may be found in [Section 5](#).

### 3 Evaluation of Trial Success and Futility

Interim monitoring will occur after the first 30 patients are on study for 16 weeks, then every 13 weeks thereafter till study enrollment closure. At each interim data review, the groups will be evaluated for early futility and early success by comparing posterior quantities for the response rate to pre-specified early stopping criteria.

#### 3.1 Early Futility

If there is less than 10% probability that the response rate in a group exceeds the historical rate  $R_g$ , then the group will stop enrollment early for futility. Formally, enrollment will stop early for futility if:

$$\Pr(\pi_g > R_g) < 0.10.$$

A group is only eligible for early stopping once a minimum of 10 patients has been evaluated for response in that group.

#### 3.2 Early Success

If there is at least 95% probability that the response rate in a group exceeds the historical rate, then the group will stop enrollment early for success. Formally, enrollment will stop early for success if:

$$\Pr(\pi_g > R_g) > 0.95.$$

A minimum of 15 subjects will need to be evaluated prior to declaring a group to be efficacious.

#### 3.3 Final Analysis

In addition, recall the final analysis will occur when both accrual and follow-up are complete in all groups. If, at the completion of the trial, there is at least 80% probability that the response rate in a group exceeds the historical rate, then the group will be considered a success. Formally:

$$\Pr(\pi_g > R_g) > 0.80.$$

## 4 Simulation

We evaluated type I error and power for each of the 8 possible groups under a variety of possible “truths” indicating various possible true underlying probabilities within each group.

### 4.1 Assumptions

Accrual – Two scenarios for the assumed two-year expected accrual are investigated: 1) 10 subjects per group and 2) 5 subjects per group. Note that these are averages, the actual number of available patients is simulated as a Poisson distribution with the specified mean. Also note that the group cap of 30 applies, and thus if the number of available patients in a group exceeds 30, only the first 30 available patients in that group will be enrolled in the study.

Dropouts – We assume no dropouts for the purpose of this simulation.

Control Rates – Table 4.1.1 shows the assumed control clinical benefit rates for each group.

**Table 4.1.1 Assumed control rates**

Tumor Type	Assumed Control Rate ( $R_g$ )
Lung NSC	0.45
Bladder	0.47
Breast	0.50
Colorectal	0.38
GIST	0.50
HNSCC	0.45
Ovarian	0.47
Sarcoma	0.40

Table 4.1.1 – Assumed control CBR values used in the simulations.

We consider four possible scenarios, or possible “truths” in the simulation. These consisted of a null scenario (where the treatment has no effect for any group), an alternative scenario (where the treatment is effective in all groups), a scenario where the treatment was effective in two of the groups, and a scenario where the treatment was effective in half of the groups.

Treatment Rates - The treatment rates for each scenario are shown in the [Table 4.1.2](#). Values identical to the control are shown in bold, while values greater than the assumed control rate are italicized.

**Table 4.1.2 Treatment rates**

	Null	Alternative	Two	Half
Lung NSC	0.45	0.71	0.45	0.45
Bladder	0.47	0.73	0.47	0.47
Breast	0.50	0.75	0.50	0.50
Colorectal	0.38	0.65	0.38	0.38
GIST	0.50	0.75	0.50	0.75
HNSCC	0.45	0.71	0.45	0.71
Ovarian	0.47	0.73	0.73	0.73
Sarcoma	0.40	0.67	0.67	0.67

Simulation Details – For each scenario we simulated 1000 trials. For each interim within each trial, we ran 50,000 MCMC iterations after a 1,000 MCMC iteration burnin.

## 4.2 Results

A total of 8 scenarios were simulated (two accrual scenarios and four possible ‘truths’ for the clinical benefit rate). The probability of group success for each group is provided for each scenarios in the tables below.

**Table 4.2.1 Probability of group success for each cohort assuming expected accrual of 10 subjects/cohort**

Two-year expected accrual: 10 subjects/cohort				
Group(Exp N)	Null	Alternative	Two	Half
Lung NSC	0.158	0.915	0.208	0.305
Bladder	0.131	0.918	0.232	0.322
Breast	0.147	0.909	0.233	0.312
Colorectal	0.138	0.921	0.200	0.276
GIST	0.162	0.921	0.233	0.826
HNSCC	0.139	0.906	0.217	0.834
Ovarian	0.145	0.929	0.786	0.829
Sarcoma	0.135	0.939	0.758	0.852

**Table 4.2.2 Probability of group success for each cohort assuming expected accrual of 5 subjects /cohort**

Two-year expected accrual: 5 subjects/cohort				
Group	Null	Alternative	Two	Half
Lung NSC	0.132	0.803	0.204	0.258
Bladder	0.140	0.830	0.196	0.265
Breast	0.160	0.807	0.232	0.261
Colorectal	0.135	0.794	0.194	0.278
GIST	0.155	0.826	0.212	0.688
HNSCC	0.140	0.820	0.190	0.657
Ovarian	0.151	0.819	0.587	0.652
Sarcoma	0.139	0.799	0.579	0.667

Entries in bold represent groups where the treatment effect is 0 (e.g. the treatment is ineffective). Thus, entries in bold are type I errors. Italicized entries appear where the treatment is effective, and thus indicate the power of the design.

Generally, type I error is controlled at 0.20 under the null scenario (the borrowing compensates for the multiple interim data reviews) and power is an increasing function of the expected sample size (power is higher in the higher accrual situation across treatment rate scenarios). In the alternative scenario there remains decently high probability of success even in the lower enrolling groups. When fewer groups are effective in truth, the scenarios “half” and “two” are harder to discern. Note in any particular trial there should be a mix of high and low enrolling cohorts, thus some cohorts may enroll closer to 10 subjects while other may only enroll five. This would produce a power value somewhere between the two tables.

Power is reduced and type I error is inflated when the truth is a mixture of effective and ineffective treatment effects across the cohorts. Generally power is a function of the sample size.

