## 10.8 Sample size calculation

The sample size was chosen by the usual criteria of obtaining adequate power for the alternative hypothesis of interest as shown in [Table 4.2.1](#) and [Table 4.2.2](#) of [Appendix R](#). This hypothesis corresponds to a generally effective treatment across groups and incorporates variation in treatment effects to reflect the realistic expectation that treatment effects may differ by group. In this setting, analytical power calculations are not possible, but the design was simulated to obtain the power of the study as shown in the appendix. The sample sizes shown (minimum of 10 for futility stopping, minimum of 15 for early success and maximum of 30 as a group cap) achieve adequate power for the alternative hypothesis. The simulations

included the expected variable accrual by simulating a Poisson process with expected accrual also shown in the appendix.

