8.1.2 Trial Logistics

The trial will enroll all available patients in all cohorts for 2 years unless a cohort cap is reached or a cohort is stopped early, or the trial is stopped early by Novartis. The trial will enroll no more than 30 evaluable patients in each cohort. Interim monitoring will be conducted starting after the first 30 patients are enrolled overall (across all cohorts), and continuing each 13 weeks thereafter till study enrollment closure. After that, one CBR analysis will be done at the end of the study. At each interim data review, response information for the various groups will be evaluated to determine the current $\Pr(\theta_g > 0 | \text{data})$ within each cohort, with sufficiently high/low values used to stop the cohort for success/futility. A minimum of 10 patients will be required in a cohort before it may discontinue enrollment for futility, and a minimum of 15 patients are required before discontinuing a cohort for efficacy. If a cohort stops enrolling early, the remaining cohorts will continue until the end of 2 years or until the other groups reach their own early stopping criteria. The final analysis will occur after the analysis of the study data for the primary CSR.

The trial will enroll patients in all listed cohorts. In addition, should other cohorts be identified throughout the trial, the following mechanism will be used. If another cohort is identified, it will not be placed into the statistical analysis unless 3 patients enroll within the cohort (thus, the trial may enroll multiple possible cohorts within the “other” category, but a cohort will only be added to the list if at least 3 patients enroll from that cohort). Thus, it is possible (but not viewed as likely) that multiple additional cohorts may be added to the trial if the trial has sufficient enrollment in multiple additional cohorts. In addition to sufficient enrollment, the sponsor must have a reasonable estimate of the control clinical benefit rate.

Patients within any cohort which does not reach the minimum 3 patient enrollment will be excluded from the interim and final analyses. As the study continues, early interim data reviews may be based on fewer cohorts than later interim data reviews, as the interim data reviews will include whatever cohorts have satisfied the criteria at the time of the data review.

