8.4.2 Results

A total of 8 scenarios were simulated (two accrual scenarios and four possible ‘truths’ for the clinical benefit rate). The probability of group success for each group is provided for each scenarios in the tables below.

Table 2.1 Probability of group success for each cohort assuming expected accrual of 10 patients/cohort

Two-year expected accrual: 10 patients/cohort				
Group(Exp N)	Null	Alternative	Two	Half
Lung NSC	0.158	0.915	0.208	0.305
Bladder	0.131	0.918	0.232	0.322
Breast	0.147	0.909	0.233	0.312
Colorectal	0.138	0.921	0.200	0.276
GIST	0.162	0.921	0.233	0.826
HNSCC	0.139	0.906	0.217	0.834
Ovarian	0.145	0.929	0.786	0.829
Sarcoma	0.135	0.939	0.758	0.852

Table 2.2 Probability of group success for each cohort assuming expected accrual of 5 patients /cohort

Two-year expected accrual: 5 patients/cohort				
Group	Null	Alternative	Two	Half
Lung NSC	0.132	0.803	0.204	0.258
Bladder	0.140	0.830	0.196	0.265
Breast	0.160	0.807	0.232	0.261
Colorectal	0.135	0.794	0.194	0.278
GIST	0.155	0.826	0.212	0.688
HNSCC	0.140	0.820	0.190	0.657
Ovarian	0.151	0.819	0.587	0.652
Sarcoma	0.139	0.799	0.579	0.667

Entries in bold represent groups where the treatment effect is 0 (e.g. the treatment is ineffective). Thus, entries in bold are type I errors. Italicized entries appear where the treatment is effective, and thus indicate the power of the design.

Generally, type I error is controlled at 0.20 under the null scenario (the borrowing compensates for the multiple interim data reviews) and power is an increasing function of the expected sample size (power is higher in the higher accrual situation across treatment rate scenarios). In the alternative scenario there remains decently high probability of success even in the lower enrolling groups. When fewer groups are effective in truth, the scenarios “half” and “two” are harder to discern. Note in any particular trial there should be a mix of high and low enrolling cohorts, thus some cohorts may enroll closer to 10 patients while other may only enroll five. This would produce a power value somewhere between the two tables.

Power is reduced and type I error is inflated when the truth is a mixture of effective and ineffective treatment effects across the cohorts. Generally power is a function of the sample size.

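### The power stated at 5 patients per cohort (0.79–0.83) cannot be the unconditional power under the plan's 3-patient minimum, which is about 0.7 if excluded cohorts count as not successful

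*Protocol*

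**What the plan says.** **Cohort size.** Protocol Appendix R Section 4.1: "Two scenarios for the assumed two-year expected accrual are investigated: 1) 10 subjects per group and 2) 5 subjects per group". These are averages; "the actual number of available patients is simulated as a Poisson distribution with the specified mean". Also: "We assume no dropouts for the purpose of this simulation".

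**Minimum size.** Appendix R Section 1.2: "Subjects within any cohort which does not reach the minimum 3 subject enrollment will be excluded from the interim and final analyses". SAP Section 8.1.2 has the same rule: "Patients within any cohort which does not reach the minimum 3 patient enrollment will be excluded from the interim and final analyses".

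**Result.** Appendix R Table 4.2.2 ("Probability of group success for each cohort assuming expected accrual of 5 subjects /cohort") and SAP Table 2.2 ("Probability of group success for each cohort assuming expected accrual of 5 patients /cohort") carry identical values. The text below each table treats entries for ineffective cohorts as type I errors and entries for effective cohorts as power. Neither table states a condition on cohort size.

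**Use.** Protocol Section 10.8 points to Tables 4.2.1 and 4.2.2 and says of the chosen sizes: "minimum of 15 for early success and maximum of 30 as a group cap) achieve adequate power for the alternative hypothesis". SAP Section 7 repeats this.

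**Silence.** The simulation assumptions cover accrual, the cap of 30, dropouts, control and treatment rates, and MCMC settings. They do not mention the 3-patient minimum.

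**The concern.** A reader will take Table 4.2.2 as the chance that a truly active cohort, planned at 5 patients, ends as a success. Under the exclusion rule a cohort with 0, 1 or 2 patients is never tested against the 0.80 posterior threshold. If such cohorts are common and the table does not count them as non-successes, the stated power is too high for that purpose. At stake is the low-accrual half of the sample size justification, and the remark in Appendix R Section 4.2 that lower-enrolling groups keep a decent chance of success.

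**Working it through.** **1. Share of cohorts below 3**

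- Mean 5: P(N<3) = e^-5 × (1 + 5 + 12.5) = 0.1247, so P(N≥3) = 0.8753.
- Mean 10: P(N<3) = e^-10 × (1 + 10 + 50) = 0.0028.

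**2. Means of the plan's own figures**

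- Alternative, 5 per cohort: (0.803 + 0.830 + 0.807 + 0.794 + 0.826 + 0.820 + 0.819 + 0.799)/8 = 0.812.
- Alternative, 10 per cohort (Table 4.2.1): 7.358/8 = 0.920.
- At 5 per cohort, effective cohorts under Half: 2.664/4 = 0.666. Under Two: (0.587 + 0.579)/2 = 0.583. Null: 1.152/8 = 0.144.

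**3. Can 0.812 be unconditional under the rule?**

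Unconditional success = P(N≥3) × success among analysed cohorts. This would need 0.812/0.8753 = 0.928 among analysed cohorts. Those cohorts average (5 − 1×0.0337 − 2×0.0842)/0.8753 = 5.5 patients. They would have to succeed at least as often as cohorts averaging 10 (0.920), whereas Appendix R Section 4.2 says power rises with expected size. The margin of 0.928 over 0.920 is small; the argument rests on the required rate not falling at all when cohort size is nearly halved.

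**4. Re-implementing the printed model**

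Inputs, all from Appendix R Sections 3 to 5: eight cohorts with the tabled rates, Poisson sizes, Dirichlet process clustering with α = 2, μ ~ N(0, 1.82), τ² ~ IG(3, 0.5), success if Pr(θ_g > 0 | data) > 0.80. The plan does not say whether 1.82 is a variance or an SD, so both were run. Read as a precision, it gives 0.747 with no minimum, which does not match the table, so that reading was set aside.

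Check at 10 per cohort, where the rule hardly acts: 0.916 to 0.93, against 0.920 tabled.

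At 5 per cohort:

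| Scenario | Table 4.2.2 mean | No minimum | Minimum 3, all cohorts counted | Minimum 3, analysed cohorts only |
|---|---|---|---|---|
| Alternative | 0.812 | 0.786–0.805 | 0.69–0.72 | 0.79–0.83 |
| Half, effective cohorts | 0.666 | 0.659 | 0.59–0.60 | 0.592/0.8753 = 0.68 |
| Two, effective cohorts | 0.583 | 0.554 | 0.51–0.54 | 0.511/0.8753 = 0.58 |
| Null | 0.144 | 0.139 | 0.11–0.135 | 0.143 |

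Single values use 1.82 as a variance. Monte Carlo error on the eight-cohort means is below 1.5 points. Most runs used the final analysis only; a run with interim looks gave 0.708 for Alternative with the minimum applied.

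**5. Where the difference comes from**

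In one run without the minimum (1.82 as SD, Alternative), cohorts of size 0, 1 and 2 made up 0.008, 0.033 and 0.089 of cohorts and were declared successes at rates 0.514, 0.631 and 0.656. Their contribution is 0.008×0.514 + 0.033×0.631 + 0.089×0.656 = 0.083. Removing it takes 0.799 to 0.716.

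**The case against.** **The table may be conditional.** Success among analysed cohorts only (0.79–0.83) fits the tabled 0.812 as well as the no-minimum runs do. A reader might infer that the simulation ignored the exclusion rule. The documents do not support that: they are silent on how small cohorts were handled, and both readings reproduce the table. This objection stands, but a conditional table needs a label before it can serve as the power of a planned cohort.

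**An excluded cohort is not a failed test.** No decision is made on it, so one may call it an accrual shortfall rather than lost power. That is a fair choice of definition, and the 0.7 figure depends on the other choice. Reporting both figures resolves it.

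**The rule may cover only added cohorts.** The exclusion sentence follows text about cohorts identified during the trial. Its own wording has no such limit, but the scope is arguable. If the listed cohorts were exempt, a listed cohort with one or two patients would be declared a success about 0.63 to 0.66 of the time under the Alternative, largely through borrowing. The plan should then say so.

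**The 5-per-cohort case is peripheral.** Protocol Section 5.1 plans 70–90 patients, which over eight cohorts is 70/8 = 8.75 to 90/8 = 11.25 each, close to Table 4.2.1. The eight cohorts are examples in a framework shared across modules. This stands and limits the severity.

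**Two further readings to avoid.** Appendix R Section 1 has a minimum of 4, but it concerns other tumor types and should not be applied to the eight simulated cohorts. Nor is there a threat to type I error: counting excluded cohorts as non-successes lowers the Null figure.

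**Conclusion.** The point holds as a mislabelled or incomplete power statement, not as a proven simulation error. Under the exclusion rule as worded, 0.79–0.83 is not the probability that a planned active cohort is declared a success. That probability is about 0.7 (0.69–0.72), so such a cohort would be missed about 28–31% of the time rather than the 19% implied by the tabled mean. The gap of about 10 points is well beyond simulation error.

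This rests on three assumptions: the rule covers the listed cohorts, excluded cohorts count as not successful, and 1.82 is a variance or an SD. The last moves the result by only about one point. At 10 per cohort only 0.3% of cohorts fall below the minimum, so Table 4.2.1 is unaffected for practical purposes. Severity is moderate.

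**What to change.** - Re-run the sponsor's own simulation with the 3-patient exclusion applied.
- In Table 4.2.2 and SAP Table 2.2, report two labelled figures per cohort: the unconditional probability of success, with excluded cohorts counted as not successful (expected to be about 0.7 under the Alternative), and the probability among analysed cohorts (about 0.8). The sponsor's run should supply the values; the figures here show only what to expect.
- State in Appendix R Section 1.2 and SAP Section 8.1.2 whether the minimum applies to the listed cohorts, and in Section 4.1 and SAP Section 8.4.1 how it enters the simulation.
- Amend protocol Section 10.8 and SAP Section 7 to cite the unconditional figure for the 5-per-cohort case.

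The cost is one simulation re-run, some text changes and a less favourable stated power at low accrual. No extra patients are needed.
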